The number of hospital readmissions (related to failure to thrive or cyanosis) may imply the overall clinical stability of a patient. Because these infants are at high risk for mortality at home, there are multiple reasons why they may be admitted to the hospital including clinically significant anemia which requires blood transfusions, poor weight gain, difficulty feeding, inadequate oxygen saturations, and illnesses. Each admission is stressful to the patient and their families. Having a normal hemoglobin level may have a role in preventing several of these factors, especially regarding failure to thrive or cyanosis.

D Investigational Agent

D1 Preclinical Data

Epoetin alfa is approved for use by the US Food and Drug Administration. The current labeled use is to treat a lower than normal number of red blood cells (anemia) caused by

chronic kidney disease in patients on dialysis to reduce or avoid the need for red blood cell transfusions. It should not be used in place of emergency treatment for anemia (red blood cell transfusions). It has not been proven to improve quality of life, fatigue, or well-being.

Common side effects include joint pain, muscle pain, bone pain, fever, cough, rash, nausea, vomiting, soreness of mouth, itching, headache, redness and pain in the injection site.

More serious side effects such as stroke, seizures, antibodies to Epoetin alfa, and serious allergic reactions have also been reported.

D2 Clinical Data to Date

There is no published clinical data on erythropoietin administration in the cyanotic congenital heart defect infant population that we are aware of.

D3 Claim for Exclusion of Environmental Assessment

In accordance with 21 CFR 25.31(e), I, [name] request a categorical exclusion from the requirement for an environmental assessment for the manufacture and formulation of *epoetin alfa* for use in human clinical trials under this IND #129795. All waste from the investigational drug will be properly controlled. The amount of wasted expected to enter the environment may reasonably be expected to be non-toxic. To my knowledge, no extraordinary circumstances exist.

D4 Dose Rationale and Risk/Benefits

500 units/kg/injection (SQ) and oral ferrous sulfate (iron) at 3 mg/kg/day (Donato 2005 & Maier 2002) which is an accepted treatment for anemia and prevention of anemia.

E Study Design

E1 Overview or Design Summary

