Informed consent will be obtained by one of the research study members after the initial surgical or catheterization procedure. Each member is well informed of the study objectives, procedures, risks, benefits, physiology of the disease process and mechanism of how the treatment works. The informed consent will be obtained from the patient's parent in a private setting. Details of the study will be presented, and ample time will be given to answer any questions. The parent will have until the eligibility period expires based on the exclusion criteria outlined above to be included in the study. Consent will be obtained in the primary language of the parent. English and Spanish versions of the consent documents will be available and official translators will be used as appropriate. An appropriate official translator will be used during the entire duration of the participant in the study. Informed consent and HIPPA authorization will be documented with the study forms that have been drafted and approved for use in the study and will be kept in a master research file for the duration of the study in a secure area, in a locked drawer by the study team. It will be made clear to the parents that participation in the study is voluntary and that decision to be included or excluded will not compromise the standard of care that the patient deserves. Patients who meet all inclusion criteria except the hematocrit of <40% will be approached and consented, but will not be formally enrolled and randomized into a study group (control or EPO) unless their hematocrit reaches <40% during their eligibility period.

2.d Randomization Method

Study subjects will be randomized 1 to 1 by an algorithm determined by the biostatistician involved. After a study subject has been enrolled into the study, a 2-digit number (1-60) will be assigned. Based on the subject number and predetermined randomization provided, a research pharmacist will dispense the study drug if the subject is enrolled in the intervention arm. This study will not be blinded.

2.e Risks and Benefits

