- Age/adjusted age
- Weight
- Oxygen saturation
- Compliance of medication
- Complete blood count
- Transfusions needed
- Hospitalizations
- Adverse events (Severity, expectedness, and relationship)

G Statistical Plan

G1 Sample Size Determination and Power

This will be a randomized controlled single center prospective study of up to 60 patients to account for drop out rate. There will be a minimum 20 treatment patients and 20 control patients enrolled. This sample size is based on a 2 proportion population formula with the assumption that without treatment about 80% of infants need transfusions (based on our experience), and 40% of infants with erythropoietin will need transfusions.

G2 Interim Monitoring and Early Stopping

Unforeseen inaccuracies in design assumptions, in particular having to do with the number of infants who need transfusions without treatment could lead to decreases in the trial's statistical power to detect treatment effects. Accordingly, an analysis will be conducted to estimate the variance of the estimated difference, between the two arms in regards to number of transfusions. This analysis will be conducted within the intention-to-treat framework under which the primary analysis of the primary endpoint will be conducted.

To allow time for corrective action if necessary, this analysis will be performed approximately after 10 patients have been enrolled in both arms. If necessary, this method will be used to obtain a recommended increase in sample size.

An interim analysis of futility will also be performed to determine if the study should continue. This will be done when 10 subjects in each arm have completed the study. The study will be terminated if there is no absolute decrease in number of transfusions per subject.

It is possible that the DSMB may consider it necessary to stop the trial early due to safety concerns. To monitor safety, adverse event rates will be compared between the two trial arms and reported to the DSMB.

In addition, the research team will perform an analysis after the first 5 subjects have completed at least 1 intervention in the EPO arm for safety. These 5 patients will serve as a safety population study.

An interim analysis of safety will be done after 10 patients have enrolled and completed each arm to assess any differences in adverse events between the 2 arms. This will be reviewed by the DSMB who will make the determination as to whether any safety concerns mandate early trial termination.

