G3 Analysis Plan

All primary analyses for efficacy will be performed on an intention-to-treat basis. All subjects will be analyzed according to their group assignment regardless of actual treatment received. In addition, both groups will be compared for safety at the end of the study by comparing adverse events and rates of adverse events. In the safety analysis, subjects will only be included if they actually received treatments in that group. (i.e. if a patient on the EPO arm did not get EPO, they should not be included in the analysis of safety in that arm).

G4 Statistical Methods

All data will only be gathered during the period in which the subjects will be active in the study (from baseline to 14 weeks post initial injection).

For the primary aim, we will compare the number of blood transfusions (one 10 ml/kg aliquot = 1 transfusion) between the two groups with a two-proportion z test. With $n = 20$ subjects per group, this test will have 80% power at the $\alpha = 0.05$ significance level to detect a difference. The primary aim will be assessed when all subjects have completed week 14.

We will compare weight gain and the change in oxygen saturation between baseline measurements and the 6 week follow-up with a two sample t-test. We will also use a linear mixed effects model, with a random intercept included to account for within subject correlation, to determine differences in the longitudinal trends in weight and oxygen saturation between groups. The length of the initial stay will be compared between groups with a two-sample t-test. We will treat the number of re-admissions (in regards to failure to thrive and cyanosis) as a categorical variable, and use Fisher's exact test to determine if there is a difference between EPO and control group readmission counts. We will consider the Mann-Whitney U test as a robust alternative to the two-sample t-test if the assumptions of the t-test are not met by the data.

With a sample size of $n = 20$ subjects per group, the t-tests described above will have 80% power at the $\alpha = 0.05$ level to detect an effect size equal to 0.91 times the common standard deviation. For weight change, assuming that the standard deviation of weights at baseline and the 6 week follow-up equal 1.22 and 1.53 (respectively), and assuming a

moderately high correlation between weight measurements within child of $\rho = 0.70$, this translates to a detectable difference of 1.00 kgs.

G5 Missing Outcome Data

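### Readmission counts are to be tested with Fisher's exact test, which ignores their order; a permutation Mann-Whitney test costs nothing and gains from about 1 to 30 points of power, depending on a readmission rate the plan does not give.

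*Combined protocol and SAP*

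**What the plan says.** Section C2 lists readmissions for failure to thrive or cyanosis among the secondary outcomes. Section C3 gives the reason: "The number of hospital readmissions (related to failure to thrive or cyanosis) may imply the overall clinical stability of a patient". It adds that a normal hemoglobin level might help prevent some of the causes of admission, so the question has a direction.

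Section G4 sets the analysis: "We will treat the number of re-admissions (in regards to failure to thrive and cyanosis) as a categorical variable", and the plan will "use Fisher's exact test to determine if there is a difference between EPO and control group readmission counts". The categories are not defined. They could be 0, 1, 2, 3 or more, or any versus none.

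A rank test appears in the same section, but only for the continuous outcomes: "We will consider the Mann-Whitney U test as a robust alternative to the two-sample t-test". No analysis that uses the order or size of the readmission counts is planned.

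On size and design, section G1 says "There will be a minimum 20 treatment patients and 20 control patients enrolled", with up to 60 infants in total. Section E2 2.d sets the ratio: "Study subjects will be randomized 1 to 1 by an algorithm". Counts run from baseline to 14 weeks after the first injection. The documents give no readmission rate, dispersion, expected effect or power for this outcome.

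**The concern.** The number of readmissions is an ordered count. Fisher's test on a table of two arms by k count categories gives the same p-value if the columns are shuffled. It therefore spreads its power over every kind of difference between the arms, including patterns that do not mean more or fewer readmissions. A significant result would not by itself say which arm did better.

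With as few as 20 infants per arm, power is scarce. A real reduction in readmissions could be missed because of the choice of test, when a test that uses the order is already named a sentence later.

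**Working it through.** **Stated figure first.** The plan gives no power for readmissions. The nearest figure is for the t-tests: "the t-tests described above will have 80% power at the $\alpha = 0.05$ level to detect an effect size equal to 0.91 times" the common SD. With 20 per arm and two-sided alpha 0.05, the noncentral t calculation gives 0.909 SD, and 80.1% power at 0.91 SD. The SD of weight change is √(1.22² + 1.53² − 2 × 0.70 × 1.22 × 1.53) = 1.103, and 0.91 × 1.103 = 1.00 kg, as stated. The plan's figures reproduce, and they fit a two-sided 0.05 test, which is used below.

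**The two tests.** Let column j hold c_j infants in all, a_j of them on EPO, with n = 20 per arm and N = 40.

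- Fisher (2 × k): the probability of a table is ∏ C(c_j, a_j) / C(N, n). The p-value sums this over all tables no more probable than the one observed. The product does not depend on column order.
- Mann-Whitney (permutation): R = Σ a_j m_j, where m_j is the midrank of column j, compared with n(N + 1)/2 = 20 × 41/2 = 410. The p-value is the exact conditional probability of a deviation at least as large. Order enters through m_j.

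**Why the rate matters.** For a Poisson mean μ, P(2 or more) = 1 − e^(−μ)(1 + μ). At μ = 0.3 this is 1 − 0.7408 × 1.3 = 3.7%, or 0.7 of 20 infants. At μ = 1.5 it is 1 − 0.2231 × 2.5 = 44.2%, or 8.8 of 20. When readmissions are rare there is little order to lose.

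**Simulation.** The means are assumptions. Both tests were run on each simulated trial with 20 per arm, at two-sided 0.05. The Fisher code matched a standard routine on 2 × 2 tables.

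| Control vs EPO mean | Fisher 2 × k | Permutation Mann-Whitney | Gap (points) |
|---|---|---|---|
| 0.3 vs 0.1 | 17% | 18% | 1 |
| 0.4 vs 0.2 | 11% | 13% | 2 |
| 0.5 vs 0.25 | 13% | 17% | 4 |
| 0.5 vs 0.2 | 21% | 26% | 5 |
| 0.6 vs 0.3 | 16% | 23% | 7 |
| 0.8 vs 0.3 | 36% | 50% | 14 |
| 1.0 vs 0.5 | 25% | 38% | 14 |
| 1.0 vs 0.4 | 39% | 55% | 16 |
| 1.2 vs 0.6 | 28% | 46% | 18 |
| 1.2 vs 0.5 | 41% | 61% | 20 |
| 1.5 vs 0.75 | 33% | 58% | 24 |
| 1.5 vs 0.6 | 51% | 75% | 24 |
| 1.5 vs 0.5 | 66% | 86% | 20 |
| 2.0 vs 1.0 | 39% | 68% | 30 |

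Gaps were taken before rounding where unrounded figures were available. Most rows rest on 5,000 trials (standard error about 0.7 points per power); 0.4 vs 0.2 and 0.6 vs 0.3 on 2,500 (about 1.0); 1.2 vs 0.5 and 1.5 vs 0.6 on 1,500 (about 1.3). Repeat runs moved gaps by a few points: 0.8 vs 0.3 also gave 13, and 1.2 vs 0.5 also gave 17. A steeper assumed reduction, 0.6 vs 0.1, gave 61% vs 71%, a gap of 9.

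**Under the null** (both means 1.0, then both 0.5; 5,000 trials): Fisher 5.0% and 4.6%, permutation Mann-Whitney 4.6% and 3.9%. The gain is not bought with false positives.

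**Variations.**

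- Overdispersed (negative binomial) counts: gaps of 10 (1.0 vs 0.5, shape 1), 24 (1.5 vs 0.5, shape 1), 16 (2.0 vs 1.0, shape 1) and 32 (2.0 vs 0.7, shape 2).
- 30 per arm: gaps of 4 (0.3 vs 0.1), 8 (0.5 vs 0.2), 14 (0.8 vs 0.3), 18 (1.0 vs 0.5) and 26 (1.5 vs 0.75).
- Any versus none, 2 × 2 Fisher, against the same rank test: under 1 point (0.3 vs 0.1), 18 (1.0 vs 0.5) and 40 (2.0 vs 1.0).

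**The case against.** Fisher's test is valid and is a natural choice for small samples with sparse cells. The outcome is secondary, and the plan makes no power claim for it.

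The counts may well be low. Only admissions for failure to thrive or cyanosis qualify, Visit 1 takes place in hospital (section F3), initial stays are often long (section C3), and follow-up ends at 14 weeks, so time at risk after discharge is shorter than that. At control means up to about 0.6 the rank test gains little, and in most of those scenarios both tests have poor power. The normal-approximation Mann-Whitney test looks better there (27% at 0.3 vs 0.1, against 18% for the permutation version), but with so many ties the permutation figures are the fair comparison.

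The plan says only that the variable is categorical; that the categories are unordered is inferred from the choice of test. The lack of an effect estimate is also not peculiar to Fisher's test, since a Mann-Whitney p-value supplies none either.

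All of this stands, and it limits the size and weight of the point. It does not remove it. The rank test had the higher power in every non-null scenario, and the any-versus-none reading does not help, because collapsing the counts loses power too.

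**Conclusion.** The point holds as a free improvement to a secondary analysis. Fisher's test, as planned, does not use the order of the counts. Against a permutation Mann-Whitney test with 20 per arm, the loss is about 1 to 7 points at control means of 0.3 to 0.6 readmissions per infant (up to 9 with a very large effect), about 13 to 20 at 0.8 to 1.2, and about 20 to 30 at 1.5 to 2.0. These ranges rest on assumed Poisson counts and, apart from the 0.6 vs 0.1 case, on assumed reductions of 50% to 67%.

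A reader might infer that the plan gives up more than 20 points of power. The documents do not support that: such a loss needs about 1.2 to 1.5 or more readmissions per control infant, and no rate is stated anywhere. Nor do they support a claim that the planned test is invalid, since its type I error is about 5% or below, or that the primary conclusion on transfusions is affected.

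**What to change.** In G4, replace the Fisher's test sentence with a comparison of readmission counts per infant by the Mann-Whitney test, using a permutation p-value because of the ties. Alongside it, report the readmission rate ratio, EPO to control, with its 95% confidence interval. State the denominator (for example infant-weeks at risk), and use an interval that allows for overdispersion.

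The cost is one or two sentences of SAP wording. G4 already names the Mann-Whitney test, and section F6 already collects hospitalizations, so no new data or infants are needed. Because the trial is open-label, the change should be made before anyone compares readmissions by arm.

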There are centers in the United States that have developed protocols using erythropoietin to minimize blood product transfusions before and after surgery, also referred to as "bloodless surgery"[4]. There have been retrospective studies evaluating the success of these protocols, but there are no randomized controlled prospective studies that have studied the effects of erythropoietin in patients with cyanotic heart disease in regards to transfusion prevention. There have also been multiple studies looking at the efficacy of EPO in the premature infant population (Donato 2005). In these studies, EPO has been shown to prevent blood transfusions. However, these findings did not represent a clinically significant difference for the study population in the long term. The clinical significance is enhanced in our study population, because blood transfusions may have significant implications for transplant candidacy in the future and transplant complications if needed. Last, there is a study involving infants and children with craniosynostosis showing that EPO is safe and can reduce the number of blood transfusions in a surgical group that has high risk for bleeding (Fearon 2001).

C Study Objectives

C1 Primary Aim

Congenital cyanotic cardiac patients require higher hemoglobin concentrations for optimal oxygen delivery. Prophylactic erythropoietin can prevent and/or decrease the amount of blood transfusions needed prior to surgery. We seek to investigate if erythropoietin makes a clinically significant difference in the number of transfusions given to these patients and the morbidity associated with it during the period in which the subjects will be active in the study (from baseline to 14 weeks post initial injection). The primary aim will be assessed when all subjects have completed week 14 or discontinued early.

C2 Secondary Aim

We will also look to see if administering erythropoietin makes a clinical significance in the following outcomes during the period in which the subjects will be active in the study

(from baseline to 14 weeks post initial injection): weight gain, oxygen saturations, length of initial hospital stay, and hospital readmissions (related to failure to thrive or cyanosis).

C3 Rationale for the Selection of Outcome Measures

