The *epoetin alfa* that will be used in the study will be obtained through commercial means, stored, and prepared by the research pharmacist associated with the study at Rady Children's Hospital. Based on the EPO prescribing information, benzyl alcohol has been associated with severe adverse events and death especially in the pediatric population. Only benzyl alcohol-free formulations of EPO will be used (multidose vials, single-dose vials admixed with benzyl alcohol will not be used.) When it is time to administer the intervention, the clinicians will order a dose of the medication. Based on the number assigned to the patient, a dose of epoetin alfa or an empty syringe will be prepared. A dedicated administering clinician assigned will then administer the prepared syringe either in the inpatient unit or in the cardiology clinic. The pharmacy will store, handle and prepare the study drugs according to the approved package inserts. The study drug will not be diluted in this trial. Unused portions of the drug in preservative-free single use vials will be discarded.

3.e Subject Compliance Monitoring

Compliance will be documented at each visit as the intervention will be done in the hospital or in the clinic setting. A member of the research team will be at each visit to fill out the case report form including compliance of iron therapy. The research team will be in charge of overseeing that patients return at the proper time for their clinical visits as described (see **table 1** and **table 2**)

3.f Prior and Concomitant Therapy

All patients based on the inclusion criteria will have had a surgical or interventional procedure for their cyanotic heart disease. All concomitant therapy that is standard of care for the patient will be continued.

3.g Packaging

Epoetin alfa will be obtained in its normal manufacture packaging. The study interventions will be prepared in standard fashion by the pharmacy for administration.

3.h Blinding of Study Drug

There will be no blinding in this study.

3.i Receiving, Storage, Dispensing and Return

Ordering, receiving, storage, and dispensing will be done by the pharmacy and research pharmacist per hospital standards and protocol.

F Study Procedures

F1 Screening for Eligibility

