Screening for eligibility will be done on the Acute Cardiac Unit at Rady Children's Hospital. When an infant with cyanotic congenital heart disease is identified, the patient will be screened for eligibility based on the inclusion and exclusion criteria described above.

F2 Schedule of Measurements

The schedule of measurements is listed in Table 1 and Table 2. For the treatment arm, a physical exam with oxygen saturation will be recorded weekly from baseline and weeks 1-7, 14. A complete blood count will be drawn at baseline (if not already obtained for clinical use, one week post procedure and ≤ 48 hours prior to 1st injection), weekly from weeks 2-7, and at week 14. Iron studies will be drawn at baseline and week 14 unless indicated in between. All labs will be analyzed by the Rady Children's Hospital Clinical Laboratory whether inpatient or outpatient.

The control arm will have a physical exam with oxygen saturations at baseline, week 7 and 14. A complete blood count will be drawn at baseline (if not already obtained for clinical use, one week post procedure and ≤ 48 hours prior enrollment) week 7 and week 14. Iron studies will be drawn at baseline and week 14 unless indicated in between. All labs will be analyzed by the Rady Children's Hospital Clinical Laboratory whether inpatient or outpatient.

F3 Visit 1

Visit 1 will be prior to 8 weeks of age and at least 1 week post procedure while in the hospital. After confirmation of eligibility for the study, a physical exam and oxygen saturation will be obtained, and the 1st dose of the intervention will be given by the subject's care team if in the EPO arm.

F4 Visit 2 etc.

Visit 2-14 may either be obtained in the hospital or in the clinic setting. A physical exam and oxygen saturation will be obtained. A complete blood count will be obtained weekly from weeks 2-7 in the EPO arm. A complete blood count will be obtained in the control group at week 7 or earlier if indicated by the subject's care team. Study injections will be given after the lab has been reviewed and confirmed there is no overshoot (Hct >45%). There will be a final physical exam and labs at week 14 of the study, which will complete the participation of the study.

F5 Safety and Adverse Events

5.a Safety and Compliance Monitoring

Safety and Compliance Monitoring will follow standard principles as outlined below.

5.b Medical Monitoring

i Investigator

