Serious: Fatal life threatening	Unexpected or Expected	Unrelated	Within 10 calendar days of first knowledge of event to the IRB
Serious (Suspected Adverse Reactions)	Unexpected	Related	Within 10 calendar days of first knowledge of event to the IRB
Serious	Unexpected or Expected	Unrelated	Within 10 calendar days of first knowledge of event to the IRB
Not Serious	Unexpected or Expected	Unrelated or Related	Quarterly to DSMB

The Investigator or designee will report all serious adverse events to the local IRB according to local IRB policies within 10 working days.

5.h Adverse Event Reporting Period

The adverse event reporting period will begin at the baseline assessment and will continue through 30 days after exiting the study.

5.i Post-study Adverse Event

All adverse events unresolved at the time of the subject's termination from the study will be followed by the investigators until the events are resolved, the subject is lost to follow-up, or the adverse event is otherwise explained or has stabilized. At the last scheduled contact, the investigator will instruct each subject or parent/guardian to report any event(s) occurring in the next 30 days. Any death or other clinically serious adverse event that may be related to the study drugs and that occurs at any time after a subject has discontinued study drug or terminated study participation will be recorded and reported.

5.j Pure Red Cell Aplasia

We will be monitoring CBCs weekly. According to the prescribing information, if PRCA is suspected with severe anemia (decline in hemoglobin level >0.5 to 1 g/dL per week or transfusion requirement once a week to maintain adequate hemoglobin levels), normal platelet and white blood cell count, and low reticulocyte count (<10,000/microL) we will perform assays for binding and neutralizing antibodies in those subjects by contacting the manufacturer. All ESA administration will be permanently discontinued and the FDA will be notified within 48 hours.

Any unused blood samples from the baseline lab draw through week 14 will be banked either at UC San Diego or Rady Children's Hospital San Diego biorepositories under appropriate conditions to allow for immunogenicity testing if needed until 6 months after an individual subject has completed their last injection.

F6 Study Outcome Measurements and Ascertainment

Ascertainment of the study outcome measurements and adverse events will be obtained on a case report form by a study investigator. These will include:

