As this study will have an intention to treat model, missing outcome data will default to reflect that the subject has received a transfusion. In addition, there may be additional analysis only reflecting subjects who have completed the study in its entirety.

H Data Handling and Record Keeping

H1 Confidentiality and Security

All data will be kept secure through the UCSD REDCap database provided by the Clinical and Translational Research Institute. REDCap is a customizable secure Web based database. It can only be accessed with a username and password that is assigned specifically to each research member. Information entered into the data entry system will be by subject study I.D. number. Data will be checked by an automated validation tool on REDCap to ensure proper data entry. A project has been created in that database for this particular study.

H2 Training

Before the study is started, each member must complete certification requirements to conduct research and show demonstration of familiarity with study procedures, methods for endpoint measurement, use of the database management system to conduct the study.

H3 Case Report Forms and Source Documents

The case report forms (both inpatient and outpatient) will be used as the source documents. The case report form that will be used can be found in section L3.

H4 Records Retention

All data will be kept secure through the UCSD RED Cap database. Hard copies of the case report forms will be stored in binders that will be kept in secure areas in the research office.

I Study Monitoring, Auditing, and Inspecting

I1 Study Monitoring Plan, Auditing and Inspecting

Interim monitoring will be performed as outlined in section G2. In addition, throughout the entire study, data will be collected and compiled on a weekly basis. Data will be entered into the database at least monthly. The research team will review to ensure that the data is being obtained properly, entered into the database properly and to look for any missing data at least quarterly. A safety report will be submitted to the DSMB for review at least quarterly.

J Study Administration

J1 Organization and Participating Centers

University of California, San Diego
Rady Children's Hospital, Heart Institute

J2 Funding Source and Conflicts of Interest

This study is currently funded by the Academic Enrichment Grant from the Rady Children's Hospital foundation.

J3 Committees

Research team:

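### Take transfusions from the hospital record in both arms: the case report form is the source document, and mandated follow-up visits are eight for EPO against two for controls

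*Combined protocol and SAP*

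**What the plan says.** - **Recording.** F6: "Ascertainment of the study outcome measurements and adverse events will be obtained on a case report form by a study investigator". The items listed include "Transfusions needed" and, separately, hospitalizations. E3 3.e sets the occasion: "A member of the research team will be at each visit to fill out the case report form including compliance of iron therapy".
- **Source.** H3: "The case report forms (both inpatient and outpatient) will be used as the source documents".
- **Visits.** F2, EPO arm: "For the treatment arm, a physical exam with oxygen saturation will be recorded weekly from baseline and weeks 1-7, 14". F2, controls: "The control arm will have a physical exam with oxygen saturations at baseline, week 7 and 14". Table 2 leaves control examinations and blood counts before week 7 to the care team's discretion.
- **Blinding.** None (E2 2.d and E3 3.h).
- **Aim.** C1 concerns the "number of transfusions given to these patients" from baseline to week 14. G4 counts each 10 ml/kg aliquot as one transfusion.
- **Missing outcomes.** G5: "missing outcome data will default to reflect that the subject has received a transfusion".

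No section that can be read says that transfusions are taken from, or checked against, the hospital's transfusion-service record. Most of the form in L3 was not available. Only its adverse-event checklist is visible, and that asks about events since the last visit.

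**The concern.** The scheduled opportunity to record the primary outcome differs by arm. An EPO infant is seen by the study team every week through week 7. A control infant may go seven weeks between mandated contacts, twice. A control transfusion given in between reaches the dataset only if someone opens an inpatient form, if it is reported as an event, or if it is picked up at the next visit. A transfusion at another hospital is the most exposed case.

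Under-recording confined to controls lowers the control rate and shrinks the apparent benefit of EPO. It would push the G2 futility look the same way, because that rule stops the trial when there is no absolute decrease in transfusions per subject.

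G5 raises a second, separate issue. An infant whose outcome is missing from the forms is scored as transfused, even if the hospital record would show no transfusion.

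**Working it through.** **1. Visit counts.** From F2 and Tables 1 and 2, mandated post-baseline visits are weeks 1, 2, 3, 4, 5, 6, 7 and 14 for EPO (8) and weeks 7 and 14 for controls (2).

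**2. The plan's own figure.** G1 assumes 80% transfused without EPO and 40% with it. G4 states 80% power with 20 per group at alpha 0.05; it does not state sidedness, so two-sided is assumed here. The unpooled formula gives

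n = (1.960 + 0.842)² × (0.8×0.2 + 0.4×0.6) / 0.4² = 7.851 × 0.40 / 0.16 = 19.6, so 20 per arm.

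Normal-approximation power at n = 20 is 80.7%, so the plan's figure reproduces. Exact enumeration over all pairs of binomial outcomes gives 75.3% for the pooled z test and 81.5% for the unpooled one. G4 does not say which version will be used, so both are shown.

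**3. Illustration of unequal capture.** Let u be the share of transfused controls recorded as untransfused, with EPO capture complete. The observed control rate is 0.80 × (1 − u), against 0.40. The documents give no value for u; the values below are assumptions.

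| u | Control rate | Difference | Exact power, pooled | Exact power, unpooled |
|---|---|---|---|---|
| 0 | 80% | 40 points | 75% | 82% |
| 5% | 76% | 36 points | 64% | 73% |
| 10% | 72% | 32 points | 52% | 63% |
| 20% | 64% | 24 points | 31% | 42% |

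On this proportion scale, a control counts as missed only if every transfusion that infant had goes unrecorded. If transfusions are analysed as a count, as C1 and G4 also suggest, each one missed matters.

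**4. The G5 default.** Suppose a share m of infants in each arm has a missing outcome and would otherwise have had the planned rates. The scored rates become 0.80 + 0.20m and 0.40 + 0.60m.

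- m = 10%: 82% against 46%, unpooled normal-approximation power 72.5%.
- m = 20%: 84% against 52%, power 63.7%.

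These losses can be avoided wherever the hospital record would supply the answer. If missingness fell on controls alone, the default would instead favour EPO. With 10% of controls missing and no true effect, the chance of a false finding for EPO rises from about 2.5% to between 3.6% and 5.3%, for true rates from 80% down to 40%. The two mechanisms therefore need not pull the same way, and no net direction can be claimed.

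**The case against.** The strongest reply is that the mandated visits are not the only route by which a transfusion is recorded.

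- H3 names an inpatient form, and C3 says transfusion requires hospitalization, so the event occurs where that form applies.
- F6 lists hospitalizations as a separate item.
- F5 5.d counts inpatient hospitalization or its prolongation as a serious adverse event, and 5.g requires reports whatever the expectedness or relationship.
- F5 5.f encourages families to report events at once rather than wait for a visit.
- I1 has data collected and compiled weekly, with a check for missing data at least quarterly, and makes no distinction by arm.
- The trial is at one center, and its research team includes treating clinicians.

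Most of this stands. The seven-week intervals are gaps between mandated examinations, not proven gaps in capture. What remains is narrower. No visible section says who opens an inpatient form for a control readmitted between visits, or how care at another hospital is learned of. A transfusion that does not prolong the initial stay need not be a serious adverse event. A transfusion never entered on a form leaves no blank field for a missing-data check to find.

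Three stronger readings are tempting, and the documents do not support them. A reader might infer that each missed form is scored as a transfusion; G5 speaks of a subject's missing outcome, and a later or inpatient form could still supply it. A reader might infer that errors could never be found because the form is its own source; the hospital chart still exists. A reader might take "Transfusions needed" in F6 to mean that a judgement is recorded instead of an event; C1, G4 and G5 speak of transfusions given or received, so this is a matter of wording only.

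**Conclusion.** The point holds as a cheap improvement, not as a demonstrated error. Scheduled ascertainment of an open-label primary outcome differs by arm (eight mandated visits against two), the form is the named source, and no visible section requires equal capture. Under-recording of control transfusions is therefore a risk of unknown size, reduced but not closed by the other routes.

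The power figures show how sensitive a trial of 20 per arm would be. They rest on assumed miss rates, complete EPO capture, the planned 80% and 40%, and a two-sided test, and they do not predict a loss. Confidence is medium, because the transfusion item on the form could not be seen and may already draw on the chart.

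**What to change.** 1. **F6 and H3.** Define the primary outcome as every red-cell transfusion given, with date and volume, taken from the hospital's transfusion-service and inpatient record. Extract it for every randomised infant over the same baseline-to-week-14 window in both arms, whether or not visits were attended. After withdrawal, do so with the family's permission, as E2 2.h provides.
2. **Care elsewhere.** At weeks 7 and 14, ask parents in both arms about care at other hospitals.
3. **G5.** Apply the default only when the record cannot be reviewed.
4. **Wording.** Align the F6 item with C1 by referring to transfusions given.

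The cost is a record extraction for 40 to 60 infants at one center, two short questions at visits already scheduled, and a small text change. No extra visits or patients are needed.
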